STATISTICAL CONSIDERATIONS	
Sample size determination: No formal sample size calculations have been performed. Sample size for this study was based upon empirical considerations.
 
Analysis population: The primary analysis population for Stage 1 and the overall study is the safety population, which is defined as all patients who received at least 1 infusion (partial or total) in the study. The primary analysis population for Stage 2 (Cohort 3) is the modified intent-to-treat (mITT) population, defined as all randomized patients in Cohort 3 who received at least 1 infusion and with evaluable baseline efficacy assessment.
 
Analysis of safety: Safety analyses will be performed using the safety population. All AEs will be coded using the most recent version of the Medical Dictionary for Regulatory Activities (MedDRA). Adverse event incidence tables will be presented by system organ class (SOC) sorted by internationally agreed order, preferred term (PT), and the number and percentage of patients experiencing an AE. Multiple occurrences of the same event in the same patient will be counted only once in the tables within a considered period. The denominator for computation of percentages is the safety population. All TEAEs, all TEAEs potentially related to study drug, all TEAEs leading to treatment discontinuation, all TEAEs that are IARs, all treatment-emergent serious adverse events (SAEs), including treatment-related SAEs, and all AEs with fatal outcome will be summarized descriptively. Additional safety data including clinical laboratory tests, vital signs, ECG, and immunogenicity will be summarized descriptively. Safety data will be summarized by cohort/treatment arm within each stage, as well as by avalglucosidase alfa dose levels (20 mg/kg, 40 mg/kg).
 
Analysis of pharmacokinetics and preliminary efficacy: PK parameters will be summarized for each visit and dose level using descriptive statistics. For each of the preliminary efficacy parameters, observed measurements and changes over time from pretreatment to post-baseline visit will be summarized by dose cohort/treatment arm within each stage and study visit using descriptive statistics. For those efficacy parameters that are used to identify patients who have sub-optimal response or clinical decline as part of inclusion criteria, patient profile (in terms of change over time) will be generated for those parameters where each patient will serve as his/her own control. Within Cohort 3, the effect of switching from alglucosidase alfa to avalglucosidase alfa will be assessed descriptively within each cohort/treatment arm using a composite score based on changes from pre-study to post 6 months avalglucosidase alfa treatment collected during the study. The control arm (alglucosidase alfa treatment) in Stage 2 will serve as a reference. The preliminary efficacy analysis will be performed within Cohort 3, based on

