11.4.3 Analyses of efficacy endpoints

Efficacy endpoints are presented in [Section 9.2.2](#).

To evaluate the effect of switching to avalglucosidase alfa after having received alglucosidase alfa at current stable dose, comparative assessment on a composite score and several other efficacy endpoints will be conducted using the mITT population in Cohort 3.

The composite score will be constructed considering 3 domains: GMFM-88 and GMFCS-E&R, ptosis, and respiratory function (the use of respiratory device). Within each domain, the change from baseline to Week 25 will be classified into improvement, unchanged, and worsening with respect to pre-defined minimally important difference in each domain. The corresponding score will be determined based on both the baseline status and the change from baseline to Week 25.

The difference in average composite scores between avalglucosidase alfa and alglucosidase alfa patients will be used as the test statistic. Due to the small sample size, statistical inference will be derived based on the re-randomization approach instead of the asymptotic approximation. Specifically, all possible randomization sequences that are consistent with the selected randomization design (matched pairs design with 5 pairs or stratified randomization stratifying on gender) will be generated, the test statistics will be calculated for all randomization sequences, and the statistical significance level will be calculated as the proportion of more or equally extreme scenarios than the observed one, among all possible scenarios.

The composite score will also be summarized descriptively by treatment group in Cohort 3.

For those efficacy parameters that are used to identify patients who have sub-optimal response or decline as part of inclusion criteria, patient profile (in terms of change over time) will be generated for those parameters where each patient will serve as his/her own control. Effect of switching from alglucosidase alfa to avalglucosidase alfa will be assessed descriptively within each cohort/treatment arm based on changes from pre-study (collected by retrospective chart review at screening/baseline) to 6 months post-avalglucosidase alfa treatment collected during the study. The control arm (alglucosidase alfa treatment) in Stage 2 will serve as a reference.

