2.1 ANALYSIS ENDPOINTS

2.1.1 Demographic and baseline characteristics

The PAP baseline value is defined as the last non-missing value prior to first investigational medicinal product (IMP) intake, unless otherwise specified.

The ETP baseline value is defined as:

- The last non-missing value prior to first IMP intake in PAP for patients receiving avalglucosidase alfa from the beginning of this study;
- The last non-missing value prior to first IMP intake in ETP for patients switching to avalglucosidase alfa from alglucosidase alfa.

Demographic characteristics

Demographic variables are age at study entry (year), gender (Male, Female), race (American Indian or Alaska Native, Asian, Black or Africa American, Native Hawaiian or other Pacific Islander, White, Not Reported), ethnicity (Hispanic, non-Hispanic, Unknown, Not Reported).

Medical or surgical history

Medical or surgical history includes prior or existing condition in different body systems as well as prior or existing medical conditions/surgical procedures of specific interest.

Disease characteristics at baseline

Pompe disease history includes acid α -glucosidase (GAA) genotyping, CRIM (cross-reactive immunologic material) status, GAA enzyme activity, [REDACTED], [REDACTED], aspects of disability (Pompe medical history, ventilator and assistive mobility device use), age at first symptoms of Pompe disease, age at diagnosis of Pompe disease, age at first treatment with alglucosidase alfa, time from Pompe disease diagnosis to first infusion of study drug, time from first symptoms of Pompe disease to first infusion of study drug.

Pompe medical history includes:

- Cardiovascular history (evidence of cardiac involvement, current NYHA (the New York Heart Association) heart failure classification, congestive heart failure),
- Ears, nose, throat medical history (enlarged tongue, hearing loss),
- Gastrointestinal (hepatomegaly, gastroesophageal reflux),
- Respiratory history (pneumonia, tracheostomy, sleep disturbances, sleep apnea),
- Musculoskeletal history (muscle weakness in upper extremities, muscle weakness in lower extremities, scoliosis, joint contractures, and current ambulatory status, assisted walking device and wheelchair use).

Family history of Pompe disease history includes confirmed Pompe disease in other family members.

Retrospective Chart Review

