Two-dimensional and M-mode ECHO will be performed and a specified medium (eg, videotape or digital) will be sent to the core central cardiology laboratory for interpretation. A central cardiologist will review all ECHO. This person will be blinded to the patient and study time point. The primary cardiac outcome assessments (measured and derived by an external vendor Biomedical Systems) to be recorded using off-line review include: LVMI, LVM Z-score, left ventricle long axis, cross sectional area, end diastolic volume, end systolic volume, internal diameter, Septal wall diameter, Posterior wall diameter, Ejection Fraction, Left Ventricle sphericity, Left Ventricle thickness:dimension ratio, and Left Ventricle mass:volume ratio. M-mode parameters include: Left Ventricle Internal Dimension, Posterior Wall, Left Ventricle Internal Dimension, and Shortening Fraction. Systolic, Diastolic, and mean blood pressure will be determined. The following Tricuspid Valve/Mitral Valve parameters will also be assessed: Right Ventricular Pressure (by TR jet), TR gradient, Mitral Valve peak E, Mitral Valve peak A, E:A Ratio, and Mitral Valve deceleration time.

Eyelid position measurements

Study participants will have images taken of their eyes while wearing a pair of empty eyeglass frames with rulers attached as a standardized measurement tool at the time points specified in

Protocol Amendment 03 Version 1 Section 1.2. The following eyelid position measurements will be performed by the central reader:

- IPFD,
- MRD-1,
- MPD.

Creatine kinase

CK measurements will come from the central lab, including both total CK and CK with MB fraction.

Composite Score Constructed Considering 3 Domains: GMFM-88 and GMFCS-E&R, Ptosis, and Respiratory Function

The exploratory composite score will be constructed considering 3 domains: GMFM-88 and GMFCS-E&R, ptosis, and respiratory function (measured by the use of respiratory device). Within each domain, the change from baseline to Week 25 will be classified into improvement, unchanged, and worsening ([Appendix A](#)), and then receives a domain score which is determined by the baseline status and the change category according to [Table 1](#). The composite score is the sum of the 3 domain scores.

Table 1- Composite Score Constructed Considering 3 Domains: GMFM-88 and GMFCS-E&R, Ptosis, and Respiratory Function

Domain	Population	Change from Baseline		
		Improvement	Unchanged	Worsening

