Patient profile (in terms of change over time starting from baseline) will be generated for all efficacy parameters where each patient will serve as his/her own control. Effect of switching from alglucosidase alfa to avalglucosidase alfa will be assessed descriptively within each study cohort and treatment arm based on changes from pre-study (collected by retrospective chart review at screening/baseline) to 6 months (Week 25) post-avalglucosidase alfa treatment using descriptive statistics. Denominators for the percentages will be based on the safety population with evaluable data on the corresponding endpoint.

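### The within-arm summary of switching runs from an undefined pre-study chart value to Week 25, so it can mix change before Day 1 with change after it

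*SAP*

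**What the plan says.** In SAP 2.4.8 the effect of the switch "will be assessed descriptively within each study cohort and treatment arm". The quantity summarised is a change over an interval that begins before study entry: "based on changes from pre-study (collected by retrospective chart review at screening/baseline) to 6 months (Week 25"). Protocol 11.4.3 has the same rule: "based on changes from pre-study (collected by retrospective chart review at screening/baseline) to 6 months post-avalglucosidase alfa treatment collected during the study".

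Chart data come from the eligibility review (protocol 7.1, criteria I 06 and I 07; SAP 2.1.1, Retrospective Chart Review). Each patient needs two or more consecutive recent assessments, separated by two weeks or longer, that document decline or sub-optimal response. Each also needs one or more assessments from before the decline began. That makes at least three chart values, and neither document says which one is the pre-study value.

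Other efficacy summaries start elsewhere:

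- Baseline, SAP 2.1.1: "The PAP baseline value is defined as the last non-missing value prior to first investigational medicinal product (IMP) intake".
- Composite score, SAP 2.1.6: "the change from baseline to Week 25 will be classified into improvement, unchanged, and worsening". Protocol 11.4.3 agrees.
- Patient profiles, SAP 2.4.8: "Patient profile (in terms of change over time starting from baseline) will be generated for all efficacy parameters". The protocol's phrase "where each patient will serve as his/her own control" belongs to these profiles, not to the pre-study change.
- By-visit summaries, protocol 11.4.3: change from baseline to each later visit, by cohort and arm.

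The protocol's Clinical Trial Summary (Statistical Considerations) conflicts with this. It describes the Cohort 3 assessment of switching as made "using a composite score based on changes from pre-study to post 6 months avalglucosidase alfa treatment collected during the study".

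**The concern.** Only change after the first study infusion can follow from the switch. A single change from a chart value to Week 25 also contains whatever happened on alglucosidase alfa between that chart value and Day 1. Patients enter because they were declining or responding poorly over that period, so the earlier part need not be near zero.

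The documents treat stabilisation as a favourable result. Protocol 9.5 counts it as evidence of a treatment effect, and SAP 2.1.6 scores it higher when the patient had been declining. Measured from a pre-decline value, the same stabilisation would appear as a loss. Measured from the latest low chart value, a rebound that owes nothing to the drug could appear as a gain. Because the start point is open in an open-label study, neither the size nor the direction of the distortion is fixed in advance.

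Cohorts 1 and 2 have no concurrent arm to set against the figure, and there it would carry the label of an effect of switching.

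**Working it through.** The documents give no effect size, SD or power for this analysis (SAP 1.3 states that no formal calculation was made), so there is no planned figure to reproduce.

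**Identity.** Change(pre-study to Week 25) = (i) change(pre-study to baseline) + (ii) change(baseline to Week 25). Only (ii) lies after the switch.

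**Within-patient size.** The input from the documents is the FVC entry criterion for Cohort 3, a relative fall of at least 15% in percent predicted (protocol 7.1, I 07). The pre-decline level is assumed.

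- From 80, baseline = 80 × 0.85 = 68.
- Stable after Day 1: Week 25 = 68. From pre-study, 68 - 80 = -12 points; from baseline, 0.
- A 10% relative gain after Day 1: 68 × 1.10 = 74.8. From pre-study, -5.2; from baseline, +6.8.
- Gain needed to read 0 from pre-study: 1/0.85 - 1 = 17.6% relative.
- A stable patient starting from 60 or 100 reads -9 or -15 (60 × 0.15; 100 × 0.15).

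These figures take the pre-decline value as the start. If the latest chart value is used and is close to baseline, (i) is near zero and most of the shortfall disappears.

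**Cohort 3 contrast.** All inputs here are assumed: 5 patients per arm, mean (i) of -12 in both arms, SD of (ii) = 5, true arm difference in (ii) = 5, and (i) uncorrelated with (ii).

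- Mean from pre-study: avalglucosidase alfa -12 + 5 = -7; alglucosidase alfa -12 + 0 = -12. Difference 5.
- Mean from baseline: +5 and 0. Difference 5.
- SE of the difference from baseline: √(2 × 5²/5) = 3.2.
- SE from pre-study: √(2 × (5² + s²)/5), where s is the SD of (i).

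| s | SE from pre-study | SE from baseline |
|---|---|---|
| 0 | 3.2 | 3.2 |
| 3 | 3.7 | 3.2 |
| 6 | 4.9 | 3.2 |
| 10 | 7.1 | 3.2 |

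A simulation of 200,000 trials gave the same means and SEs. The within-arm means shift by the full -12. The randomised difference keeps its expected value and loses precision. A negative correlation between (i) and (ii), which shared error in the baseline value would produce, would reduce that loss.

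**Regression to the mean.** Suppose the baseline shares the unusually low error e (e < 0) on which the patient was selected. Then (i) contains +e, (ii) contains -e, and the within-patient difference (ii) - (i) contains -2e. That difference is therefore the column most exposed to this artefact.

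**The case against.** The strongest reply is that this is one untested, descriptive summary of a secondary objective in a phase 2 safety study, which SAP 2.4.8.1 says is not confirmatory. SAP 2.4.8 opens by evaluating the switch through a randomised comparison in the Cohort 3 mITT population. The composite tested there, the protocol's by-visit changes and the SAP's patient profiles all start from baseline. All of this stands. A reader might infer that the trial's whole assessment of switching rests on a chart value, or that its one hypothesis test is biased. The documents do not support either. The synopsis ties the composite to pre-study change, but the two detailed definitions (protocol 11.4.3, SAP 2.1.6) use baseline.

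A reader might also infer that earlier decline is credited to avalglucosidase alfa as benefit. The text does not support that direction: with a pre-decline start, earlier loss counts against the drug.

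It can also be said that the plural in the rule may mean a trajectory rather than one subtraction, and that requiring repeated chart assessments limits selection on a single poor value. The first reading is possible but not stated. The second reduces regression to the mean without removing it. Neither tells the programmer which chart value to use.

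Finally, the chart review collects only what is available, including milestones, ptosis and other tests. Rates per unit time do not suit binary or non-comparable items. This stands and limits the fix.

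**Conclusion.** The point holds for the within-arm summary only. As written, that summary can mix change on alglucosidase alfa before Day 1 with change after it, and its start value is undefined. For a patient at the FVC entry threshold who is stable after the switch, the shortfall is 15% of the pre-decline value: -9, -12 or -15 points for assumed starts of 60, 80 or 100% predicted. This rests on taking the pre-decline chart value as the start; with the latest value, the more likely distortion is a favourable rebound.

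The consequence is greatest in Cohorts 1 and 2. In Cohort 3, randomisation makes the pre-study part equal in expectation between arms, so the contrast is not biased, although about 5 patients per arm leave room for chance imbalance. On the assumed inputs, the SE rises from 3.2 to 4.9 when the pre-study SD is 6.

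Two smaller defects should be corrected with it. The rule refers to a value after six months of avalglucosidase alfa, which the alglucosidase alfa arm does not have at Week 25 because its switch starts at Week 27. And the synopsis disagrees with the detailed sections on where the composite starts.

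**What to change.** In SAP 2.4.8 and protocol 11.4.3:

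1. Define the pre-study value, naming which of the required chart assessments is used.
2. Split the summary at Day 1, for every cohort and both Cohort 3 arms, into (i) pre-study to baseline, with assessment dates, and (ii) baseline to Week 25. Give (i) as a rate only for continuous measures with comparable repeat values.
3. Attach the label 'effect of switching' to (ii), and make the Cohort 3 between-arm difference in (ii) the basis for any claim. For the alglucosidase alfa arm, describe (ii) as change on continued treatment.
4. If a within-patient difference in slope is shown, present it as descriptive, with a caveat on regression to the mean.
5. Reconcile the protocol synopsis (composite from pre-study) with protocol 11.4.3 and SAP 2.1.6 (composite from baseline).

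The cost is a little more tabulation. Baseline-to-Week-25 changes are already planned and chart data are already collected. The limit is that part (i) can be shown only for patients with dated, comparable chart values.

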2.4.8.1 Multiplicity issues

This phase 2 study is not considered as a confirmatory clinical study. P-values will be presented without multiplicity adjustment.

2.4.8.2 Subgroup analyses

Due to the limited power in these subpopulations, selected subgroup analyses, if appropriate, may be explored using descriptive statistics or graphically by treatment group for the overall avalglucosidase alfa treatment period only.

The following baseline factors may be explored to assess their impact on efficacy with exploratory analysis: prior alglucosidase treatment duration, duration of disease, age at first alglucosidase infusion, age at first infusion of avalglucosidase alfa, gender, race, ethnicity, baseline status on invasive ventilatory support, baseline use of noninvasive ventilatory support, baseline status on assistive device use, baseline LVM Z-score, baseline GMFCS level, GAA genotyping, CRIM status, [REDACTED], quartiles of peak IgG antibody titer and status of inhibitory antibody.

2.4.9 Analyses of pharmacodynamics variables

Creatinine-normalized urine Hex4 levels (mmol/mol) will be summarized using descriptive statistics at each scheduled study visit in PD population. Observed measurements as well as the change from baseline will be summarized. If a linear trend in the change of urine Hex4 levels is observed, a longitudinal model may be employed to model change from baseline over time. In addition, 95% confidence intervals of changes will be presented.

Correlation between PK endpoints and urine Hex4 levels will be explored as appropriate.

[REDACTED]

[REDACTED]

2.4.10 Analyses of tertiary endpoints

For each of the tertiary endpoints, observed measurements and changes over time from baseline to each post-baseline visit will be summarized by study cohort and treatment arm. Denominators for the percentages will be based on the safety population with evaluable data on the corresponding endpoint. Graphical displays may be provided as appropriate.

2.4.10.1 Correlation of efficacy endpoints

In order to identify the relationship between outcomes, correlation analysis for the following efficacy endpoints (at baseline, at Week 25 and change from baseline to Week 25) might be explored graphically for all enrolled patients, regardless of cohorts or treatment arms.

Corresponding summary tables may be generated as appropriate.

- GMFM-88: total raw score, total % score
- Pompe PEDI Functional Skills Scale: Mobility Domain: raw score, normative standard score, scaled score,
- QMFT: total score
- ECHO: LVM-Z score and LVMI
- CK
- Hex4
- 6MWT: distance walked
- Pulmonary function testing: FVC (% predicted) upright, MIP (% predicted) upright, MEP (% predicted) upright
- Use of ventilator
- PedsQL generic core scale score
- PedsQL pediatric pain questionnaire score
- Pain visual analog scale
- Bayley-III Composite score
- Leiter-3 Nonverbal IQ Composite score

2.5 DATA HANDLING CONVENTIONS

2.5.1 General conventions

In general, the baseline value is defined as latest non-missing value prior to the start of first infusion in PAP or ETP ([Section 2.1.1](#)). In the case an assessment performed on the same date as the first infusion date, but it is impossible to determine the evaluation time relative to first infusion start time, the evaluation time will be assumed to follow the protocol-defined schedule.

2.5.2 Missing data handling in data presentation

In general, missing baselines will not be imputed. The following approaches are default methods for missing data handling in summary tables.

- Categorical data at baseline will be summarized for each treatment group using n and %. Denominator will be the analysis population specified for the summary, unless otherwise specified. Missing data may be presented as a separate category.

- Continuous data: The analyses and summaries for variables with continuous scales will be based on observed data only.

Handling of computation of treatment duration if investigational medicinal product end of treatment date is missing

For the calculation of the treatment duration, the date of the last dose of IMP is equal to the date of last administration reported on drug exposure e-CRF page. If this date is missing, then the duration is missing.

The last dose intake should be clearly identified in the e-CRF and should not be approximated by the last returned package date.

Handling of missing/partial dates for adverse events or concomitant medications

Missing or partial AE onset dates and times will be imputed so that if the partial AE onset date/time information does not indicate that the AE started prior to treatment or after the treatment-emergent adverse event period, the AE will be classified as treatment-emergent. No imputation of AE end dates/times will be performed. These data imputations are for categorization purpose only and will not be used in listings. No imputation is planned for date/time of AE resolution.

No imputation for medication start/end dates or times will be performed. If a medication date or time is missing or partially missing and it cannot be determined whether it was taken prior or concomitantly, it will be considered a prior, concomitant, and post-treatment medication.

Handling of missing or partial birth date for calculation of age

Complete missing of birth date is not expected for the study. However, there could be rare situations in which the birth day or month is not provided for the patient due to confidentiality. In this case, the missing day will be imputed as 15th of the month, and missing month will be imputed as June as default. The adjustment may be needed in the case of conflicting with study dates. These adjustments should be very rare and will be documented in the data specification document.

Handling of adverse events when date and time of first investigational medicinal product administration is missing

When the date and time of the first IMP administration is missing, all AEs that occurred on or after the day of randomization should be considered as TEAEs. The exposure duration should be kept as missing.

The last dose intake should be clearly identified in e-CRF and should not be approximated by the last returned package date.

Handling of missing assessment of relationship of adverse events to investigational medicinal product

If the assessment of the relationship to IMP is missing, then the relationship to IMP in the frequency tables is considered as possibly related, but no imputation should be done at the data level.

Handling of missing severity of adverse events

If the severity is missing for one of the treatment-emergent occurrences of an AE, the maximal severity on the remaining occurrences of the same patient will be considered. If the severity is missing for all the occurrences, a “missing” category will be added in the summary table.

Handling of potentially clinically significant abnormalities

If a patient has a missing baseline he will be grouped in the category “normal/missing at baseline”.

For PCSAs with 2 conditions, one based on a change from baseline value or a normal range and the other on a threshold value, with the first condition being missing, the PCSA will be based only on the second condition.

For a PCSA defined on a threshold and/or a normal range, this PCSA will be derived using this threshold if the normal range is missing; e.g., for eosinophils the PCSA is >0.5 GIGA/L or $>$ ULN if $ULN \geq 0.5$ GIGA/L. When ULN is missing, the value 0.5 should be used.

Measurements flagged as invalid by the laboratory will not be summarized or taken into account in the computation of PCSA values.

Handling of ADA titer with missing or non-numerical values

If the ADA titer is reported as “< value”, then the actual value is imputed as this value. For example, “<100” will be imputed as 100. A negative ADA status will be assumed as a value of 0 (will be excluded when geometric mean of the group needs to be calculated).

Handling of missing domains for the composite score

If any of the 3 domains including GMFM-88 and GMFCS-E&R, ptosis, and respiratory function, has missing data at baseline, the domain score of change from baseline at the end of PAP will be 0.

If data is missing at Week 25, the score measured at precedent visit (Week 13) will be used.

